16.2 ECOG Performance Status Criteria

Grade	Description
0	Normal activity. Fully active, able to carry on all pre-disease performance without restriction
1	Symptoms but ambulatory. Restricted in physically strenuous activity, but ambulatory and able to carry out work of a light or sedentary nature (e.g., light housework, office work)
2	In bed < 50% of the time. Ambulatory and capable of all self-care, but unable to carry out any work activities. Up and about more than 50% of waking hours.
3	In bed > 50% of the time. Capable of only limited self-care, confined to bed or chair more than 50% of waking hours.
4	100% bedridden. Completely disabled. Cannot carry on any self-care. Totally confined to bed or chair.
5	Dead.

Source: Oken MM, Creech RH, Tormey DC, Horton J, Davis TE, McFadden ET et al. Toxicity and response criteria of the Eastern Cooperative Oncology Group. Am J Clin Oncol 1982; 5 (6):649-55.

16.3 Contraception Requirements

Females or males of reproductive potential must agree to avoid becoming pregnant or avoid impregnating a partner, respectively. Female or males of reproductive potential are required to use adequate methods of birth control from the time of screening (i.e., at least 14 days prior to D1 of SL-172154) through at least 30 days after the last dose of SL-172154.

Definition of Female of Childbearing Potential:

A female subject who is not sterile due to surgery (i.e., from bilateral tubal ligation/occlusion, bilateral oophorectomy, bilateral salpingectomy or complete hysterectomy) or who does not have a congenital or acquired condition that prevents childbearing or who is not naturally post-menopausal for at least 12 consecutive months.

Definition of Female of Non-Reproductive Potential:

Female subjects will be considered of non-reproductive potential if they:

1. Are post-menopausal if defined as amenorrhoeic for 12 consecutive months without an alternative medical cause. In women < 45 years of age a high follicle stimulating hormone (FSH) level in the postmenopausal range may be used to confirm a postmenopausal state in women not using hormonal contraception or hormonal replacement therapy. In the absence of 12 consecutive months of amenorrhea, a single FSH measurement is insufficient;
OR
2. Have had a hysterectomy and/or bilateral oophorectomy, bilateral salpingectomy or bilateral tubal ligation/occlusion, at least 6 weeks prior to screening;
OR
3. Have a congenital or acquired condition that prevents childbearing.

Definition of Male of Non-Reproductive Potential:

Male subjects will be considered of non-reproductive potential if they have azoospermia (whether due to having had a vasectomy or due to an underlying medical condition).

Highly Effective Methods of Contraception (<1% failure rate):

For contraception, subjects should comply with one of the following:

1. Practice abstinence† from heterosexual activity;
OR
2. Use (or have their partner use) acceptable contraception during heterosexual activity.

Acceptable methods of contraception are‡:

- Single method (one of the following is acceptable):
 - intrauterine device
 - vasectomy of a female subject's male partner
 - contraceptive rod implanted into the skin
- Combination Methods
 - Female Subjects: The following hormonal contraceptives may be used by female subjects and requires use of a male condom for the male partner:
 - oral contraceptive pill (estrogen/progestin pill or progestin-only pill)
 - contraceptive skin patch
 - vaginal contraceptive ring
 - subcutaneous contraceptive injection

- Male Subjects: The following contraception methods may be used by female partners and requires use of a male condom for the male subject:
 - diaphragm with spermicide
 - cervical cap with spermicide (nulliparous women only)
 - contraceptive sponge (nulliparous women only)
 - hormonal contraceptives including oral contraceptive pill (estrogen/progestin-only pill), contraceptive skin patch, vaginal contraceptive ring, subcutaneous contraceptive injection

†Abstinence (relative to heterosexual activity) can be used as the sole method of contraception if it is consistently employed as the subject's preferred and usual lifestyle and if considered acceptable by local regulatory agencies and IRBs/Independent IECs. Periodic abstinence (e.g., calendar, ovulation, sympto-thermal, post-ovulation methods) and withdrawal are not acceptable methods of contraception.

‡If a contraceptive method listed above is restricted by local regulations/guidelines, then it does not qualify as an acceptable method of contraception for subjects participating at sites in this country/region.

Subjects should be informed that taking the study medication may involve unknown risks to the fetus (unborn baby) if pregnancy were to occur during the study. To participate in the study, subjects of childbearing potential must adhere to the contraception requirement (described above) from the time of screening and at least 14 days prior to D1 of SL-172154 through at least 30 days after the last dose of SL-172154.

16.3.1 Pregnancy Status

In the rare event that β -hCG is elevated as a tumor marker, pregnancy should be excluded. At minimum, this requires obstetrics evaluation, serial β -hCG measurements and ultrasound to exclude pregnancy.

16.4 Cockcroft-Gault Formula for Creatinine Clearance

$$\text{Creatinine clearance (mL/min)} = \frac{Q \times (140 - \text{age [yr]}) \times \text{ideal body weight [kg]}^2}{72 \times \text{serum creatinine [mg/dL]}}$$

Q = 0.85 for females

Q = 1.0 for males

OR

$$\text{Creatinine clearance (mL/min)} = \frac{K \times (140 - \text{age [yr]}) \times \text{ideal body weight [kg]}^1}{\text{serum creatinine } [\mu\text{mol/L}]}$$

K = 1.0 for females

K = 1.23 for males

1. Creatinine clearance has a maximum value of 125 mL/min.
2. Use ideal body weight (IBW) if body weight > 30% of IBW.
Otherwise, use bodyweight

Calculation of IBW using the Devine Formula [Devine, 1974]:

Males = $50.0 \text{ kg} + (2.3 \times \text{each inch over 5 ft})$ or $50.0 \text{ kg} + (0.906 \text{ kg} \times \text{each cm over 152.4 cm})$

Females = $45.5 \text{ kg} + (2.3 \times \text{each inch over 5 ft})$ or $45.5 \text{ kg} + (0.906 \text{ kg} \times \text{each cm over 152.4 cm})$

Example:

Male, actual body weight = 90.0 kg; height = 68 inches; IBW = $50 + (2.3)(68 - 60) = 68.4 \text{ kg}$

This subject's actual body weight is >30% over IBW. Therefore, in this case, the subject's IBW of 68.4 kg should be used in calculating the estimated creatinine clearance

References:

Devine BJ. Case Number 25 Gentamicin Therapy: Clinical Pharmacy Case Studies. Drug Intell. Clin Pharm. 1974;8:650-655.

Levey, A.S., J. Coresh, T. Greene, et al. (2006). Using standardized serum creatinine values in the modification of diet in renal disease study equation for estimating glomerular filtration rate. Ann Intern Med. 145:247-254.

Levey, A.S., L.A. Stevens, C.H. Schmid, et al. (2009). A new equation to estimate glomerular filtration rate. Ann Inter Med. 150:604-612.

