 - Lesions must be located in an anatomic location where SL-172154 can be safely administered and not in close proximity to critical structures (e.g., major blood vessels, nerve bundle, trachea or a major airway tract) as determined by the investigator.
 - Pharmacodynamic Cohort ONLY: Must have a second lesion that is non-injected and is amenable to tumor biopsy collection. (Note: This non-injected lesion is not required to be measurable per RECIST v1.1.)
6. Subject age is 18 years and older.

7. Has an Eastern Cooperative Oncology Group (ECOG) Performance Status of 0 or 1
8. Has life expectancy of greater than 12 weeks.
9. Laboratory values must meet the following criteria.

Laboratory parameter	Threshold value
Absolute lymphocyte count (ALC)	$\geq 0.8 \times 10^9/\text{liter (L)}$
Absolute neutrophil count (ANC)	$\geq 1.5 \times 10^9/\text{L}$ without growth factor support
Platelet count	$\geq 100 \times 10^9/\text{L}$
Hemoglobin (Hgb)	$> 9.0 \text{ g/dL}$ with no blood transfusions for at least 5 days prior to D1 of IP.
Creatinine clearance (CrCl)	$\geq 30 \text{ milliliter (mL)/min}$ (using modified Cockcroft-Gault formula; Appendix Section 16.4)
ALT/AST	$\leq 3 \times \text{ULN}$
Total bilirubin	$\leq 1.5 \times \text{ULN}$; subjects with isolated indirect hyperbilirubinemia are permitted if direct bilirubin ratio is <35% and total bilirubin is $\leq 3.0 \times \text{ULN}$
International normalized ratio (INR) and activated partial thromboplastin time (aPTT)	$\leq 1.5 \times \text{ULN}$
QTcF interval	$\leq 480 \text{ milliseconds}$

10. Females of childbearing potential (FCBP) must have a negative serum or urine pregnancy test within 72 hours of D1 of IP. NOTE: FCBP unless they are surgically sterile (i.e., have undergone a complete hysterectomy, bilateral tubal ligation/occlusion, bilateral oophorectomy or bilateral salpingectomy), have a congenital or acquired condition that prevents childbearing or are naturally postmenopausal for at least 12 consecutive months (see Appendix Section 16.3 for additional details). Documentation of postmenopausal status must be provided. FCBP should use an acceptable method of contraception (see Appendix Section 16.3) to avoid pregnancy during treatment and for 30 days (which exceeds 5 half-lives) after the last dose of IP. FCBP must start using acceptable contraception at least 14 days prior to D1 of IP.

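### Appendix 16.4 states two conflicting weight rules for creatinine clearance, so a patient near the 30 mL/min inclusion limit can be eligible under one and ineligible under the other

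*Protocol*

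**What the plan says.** Protocol Section 4.1, criterion 9 (and the synopsis), sets the limit at 30 mL/min or more, "using modified Cockcroft-Gault formula; Appendix Section 16.4". Section 4 rules out eligibility waivers.

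Appendix 16.4 prints two formulas, one for creatinine in mg/dL and one for µmol/L. Both label the weight term as ideal body weight. Note 2 then gives the weight rule: "Use ideal body weight (IBW) if body weight > 30% of IBW", followed by "Otherwise, use bodyweight". The worked example takes this subject: "Male, actual body weight = 90.0 kg; height = 68 inches". It finds an IBW of 68.4 kg and reasons: "This subject's actual body weight is >30% over IBW". It concludes that "68.4 kg should be used in calculating the estimated creatinine clearance".

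The mg/dL formula uses Q = 0.85 for women and 1.0 for men. The µmol/L formula has "K = 1.0 for females" and 1.23 for men.

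**The concern.** Note 2 and the example differ by one word, *of* against *over*, but they set very different cut-offs: 30% of IBW against 130% of IBW. Under the first, the fallback to actual weight never operates. Under the second, actual weight is used for everyone up to 130% of IBW. The two rules agree only above 130% of IBW, or when actual weight happens to equal IBW.

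CrCl is proportional to the weight used, so the choice carries straight into an eligibility decision. Ideal weight raises the result for an underweight patient and lowers it for a patient between 100% and 130% of IBW. Two sites could classify the same patient differently and both cite Appendix 16.4.

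**Working it through.** **Inputs from the documents (Appendix 16.4, Section 4.1).** Male IBW = 50 + 2.3 × (inches − 60). CrCl = Q × (140 − age) × weight / (72 × creatinine in mg/dL). The 125 mL/min cap does not bind near the limit of 30.

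**Assumed inputs, not in the documents.** The age, height, weight and creatinine of the illustrative patients.

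**1. The plan's own example.** IBW = 50 + 2.3 × 8 = 68.4 kg, as printed. 90.0 / 68.4 = 1.316, or 31.6% over IBW, so the example is correct under its own test (cut-off 1.30 × 68.4 = 88.9 kg).

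**2. Note 2 read literally.** The cut-off is 0.30 × 68.4 = 20.5 kg. For heights of 60 to 76 inches, both sexes, it runs from 13.7 to 26.0 kg (BMI about 6 to 7). No adult falls below it. The 90 kg man gets IBW under either rule, so the example's result does not expose the conflict.

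**3. Effect at the limit (assumed man aged 70, 70 inches; IBW = 50 + 2.3 × 10 = 73 kg).**

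| Weight | Creatinine (mg/dL) | Actual weight (example's rule) | IBW (note 2 literally) |
|---|---|---|---|
| 55 kg | 1.8 | 70 × 55 / 129.6 = 29.7, ineligible | 70 × 73 / 129.6 = 39.4, eligible |
| 87.6 kg (20% over IBW) | 2.6 | 70 × 87.6 / 187.2 = 32.8, eligible | 70 × 73 / 187.2 = 27.3, ineligible |

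At 55 kg the two rules disagree on eligibility for creatinine between 70 × 55 / (72 × 30) = 1.78 and 70 × 73 / (72 × 30) = 2.37 mg/dL.

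**4. Range over weight, free of age and creatinine (IBW 68.4 kg).** If CrCl is exactly 30 by actual weight, the literal rule returns 30 × 68.4 / weight: 34.2 at 60 kg, 37.3 at 55 kg, 41.0 at 50 kg, 45.6 at 45 kg. In the other direction, a literal result of 30 corresponds to 30 × weight / 68.4 by actual weight: 32.9 at 75 kg, 35.1 at 80 kg, 37.3 at 85 kg.

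**5. Female constant.** If the male constants agree across units, the female K should be 0.85 × 1.23 = 1.0455. Allowing for rounding in 1.23 (1.225 to 1.235), the range is 1.04 to 1.05. The printed 1.0 gives 1.0 / 1.0455 = 0.957, about 4% lower. A woman between 30.0 and about 30 × 1.0455 = 31.4 mL/min by the mg/dL formula would fall below 30 by the µmol/L formula.

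**The case against.** The strongest reply is that the appendix largely resolves its own slip. The example states its test in words a few lines below note 2, and the fallback to actual weight would be pointless under the literal reading. A site that follows the example uses actual weight for an underweight patient. This stands: misclassification is a risk under one reading, not the result of the appendix as a whole. It does not remove the conflict, because no example covers a patient at or below 130% of IBW, and both formulas print ideal weight. In the mg/dL formula that term carries the marker for note 2. In the text as extracted, the µmol/L term carries the marker for note 1 (the cap), though this may be an extraction artefact.

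The patients are invented, and the 55 kg man is only 0.3 mL/min below the limit. That is fair; the creatinine interval and weight range above are the better measure. With about 18 subjects planned, the number affected may be zero.

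The female constant matters only where a site reports in µmol/L, which is not shown for a study planned at US sites. Its error excludes rather than admits. It remains a secondary correction.

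SAP Section 1 records that enrolment was discontinued as of 24 February 2022, so new wording cannot change any eligibility decision already made. This also stands, and it moves the useful action to the subjects already treated.

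**Conclusion.** Appendix 16.4 contradicts itself on the weight used for an eligibility limit, and the contradiction can reverse the decision in either direction for patients near 30 mL/min. In the assumed cases the rules give 29.7 against 39.4 and 32.8 against 27.3. The size of the difference is simply the ratio of IBW to actual weight. The contradiction itself rests on the printed text alone; the patient figures are assumptions.

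A reader might infer that underweight patients below the limit were enrolled, or that the appendix always admits them. The documents do not support either: the example points to the other rule, only a limited band of values below 30 is affected, and no weight or creatinine distribution is given. A reader might also infer that anyone admitted on ideal weight is an eligibility deviation. Protocol Section 14.4 defines a deviation as noncompliance with the protocol, and a site that applied note 2 as written complied with it.

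No DLT rule, sample size or endpoint analysis is touched. The point merits correction because the criterion is decided by this number and the repair is small.

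**What to change.** - Reconcile note 2 with the worked example. The example's wording is more than 30% over IBW; note 2 and the example should state one test.
- In both formulas, label the weight term as weight in kg with a pointer to note 2, in place of ideal body weight.
- Make the female K consistent with Q = 0.85 and the male K = 1.23 (about 1.04 to 1.05).
- Recompute baseline CrCl for treated subjects from screening age, sex, height, weight and creatinine under the reconciled rule, before protocol deviations are summarised (SAP Section 6.2). List any subject whose eligibility would differ as affected by the protocol inconsistency, and do not record a deviation automatically.

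The cost is four small edits in one appendix (the note, two labels, one constant) and a recalculation from screening data that the protocol already collects. If the edits are issued as an amendment, Protocol Section 13.2 requires IRB/IEC review. With enrolment closed, the recalculation is the part with practical effect; the wording change serves the record and any reuse of the appendix.

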16.5 RECIST 1.1

16.5.1 RECIST 1.1 Criteria

Measurable disease: Measurable tumor lesions (nodal, subcutaneous, lung parenchyma, solid organ metastases) are defined as those that can be accurately measured in at least one dimension (longest diameter to be recorded) as ≥ 10 millimeter (mm) with CT scan or clinical examination. Bone lesions are considered measurable only if assessed by CT scan and have an identifiable soft tissue component that meets these requirements (soft tissue component ≥ 10 mm by CT scan). Malignant lymph nodes must be ≥ 15 mm in the short axis to be considered measurable; only the short axis will be measured and followed. All tumor measurements must be recorded in mm (or decimal fractions of cm). Previously irradiated lesions are not considered measurable unless progression has been documented in the lesion.

Malignant lymph nodes: pathological nodes must meet the criterion of a short axis of ≥ 15 mm by CT scan and only the short axis of these nodes will contribute to the baseline sum. All other pathological nodes (those with short axis ≥ 10 mm but < 15 mm) should be considered non-target lesions. Nodes that have a short axis < 10 mm are considered non-pathological and should not be recorded or followed.

Non-measurable disease: All other lesions (or sites of disease), including small lesions (longest diameter < 10 mm [< 1 cm] or pathological lymph nodes with ≥ 10 to < 15 mm [≥ 1 to < 1.5 cm] short axis), are considered non-measurable disease. Bone lesions without a measurable soft tissue component, leptomeningeal disease, ascites, pleural/pericardial effusions, lymphangitis cutis, inflammatory breast disease, lymphangitic involvement of lung or skin, and abdominal masses followed by clinical exam are all non-measurable. Lesions in previously irradiated areas are non-measurable, unless progression has been demonstrated.

Note: Cystic lesions that meet the criteria for radiographically defined simple cysts should not be considered as malignant lesions (neither measurable nor non-measurable) since they are, by definition, simple cysts.

‘Cystic lesions’ thought to represent cystic metastases can be considered as measurable lesions, if they meet the definition of measurability described above. However, if non-cystic lesions are present in the same participant, these are preferred for selection as target lesions.

Target lesions: When more than one measurable tumor lesion is present at baseline all lesions up to a maximum of 10 lesions in total, representative of all involved organs, should be identified as target lesions and recorded and measured at baseline. Target lesion selection will not be capped at a maximum of 2 lesions per organ. Target lesions should be selected on the basis of their size (lesions with the longest diameter), be representative of all involved organs, but in addition should be those that lend themselves to reproducible repeated measurements. It may be the case that, on occasion, the largest lesion does not lend itself to reproducible measurement in which circumstance the next largest lesion which can be measured reproducibly should be selected. A sum of the diameters (longest for non-nodal lesions, short axis for nodal lesions) for all target lesions will be calculated and reported as the baseline sum diameters. If lymph nodes are to be included in the sum, then only the short axis is added into the sum. At baseline, the sum of the target lesions

(longest diameter of tumor lesions plus short axis of lymph nodes: overall maximum of 10) is to be recorded.

After baseline, a value should be provided on the eCRF for all identified target lesions for each assessment, even if very small. If extremely small and faint lesions cannot be accurately measured but are deemed to be present, a default value of 5 mm may be used. If lesions are too small to measure and indeed are believed to be absent, a default value of 0 mm may be used. The baseline sum diameters will be used as reference to further characterize any objective tumor regression in the measurable dimension of the disease.

Non-target lesions: All non-measurable lesions (or sites of disease) plus any measurable lesions over and above those listed as target lesions are considered **non-target lesions** and should also be recorded at baseline. Measurements of these lesions are not required, but the presence, absence, or in rare cases unequivocal progression of each should be noted throughout follow-up.

16.5.2 Evaluation of Response

Complete Response (CR): Disappearance of target and non-target lesions and normalization of tumor markers. Pathological lymph nodes must have short axis measures <10 mm (Note: continue to record the measurement even if <10 mm and considered CR). Residual lesions (other than nodes <10 mm) thought to be non-malignant should be further investigated (by cytology, specialized imaging or other techniques as appropriate for individual cases) before CR can be accepted. Response should be confirmed in a subsequent scan ≥ 4 weeks after the scan showing CR.

Partial Response (PR): At least a 30% decrease in the sum of the measures (longest diameters for tumor lesions and short axis measure for nodes) of target lesions, taking as reference the baseline sum of diameters. Non-target lesions must be non-progressive disease. Response should be confirmed in a subsequent scan ≥ 4 weeks after the scan showing PR.

Stable Disease (SD): Neither sufficient shrinkage to qualify for PR nor sufficient increase to qualify for PD, taking as reference the smallest sum diameters while on study. Documented at least once ≥ 4 weeks from baseline.

Progressive Disease (PD): At least a 20% increase in the sum of diameters of measured lesions taking as references the smallest sum of diameters recorded on study (including baseline) AND an absolute increase of ≥ 5 mm. Appearance of new lesions will also constitute PD (including lesions in previously unassessed areas). In exceptional circumstances, unequivocal progression of non-target disease may be accepted as evidence of disease progression, where the overall tumor burden has increased sufficiently to merit discontinuation of treatment or where the tumor burden appears to have increased by at least 73% in volume. Modest increases in the size of one or more non-target lesions are NOT considered unequivocal progression. If the evidence of PD is equivocal (target or non-target), treatment may continue until the next assessment, but if confirmed, the earlier date must be used.

16.6 Summary of Changes for Amendment 01

Minor Editorial Changes

- Title page and all page headers have edits to denote revised version number /date of amendment 01
- Updated Table of Contents
- Updated Abbreviations to include definitions for ECG, QTcF, QTcB
- New Appendix added to summarize changes made for Amendment 01
- Footnotes to SOA table in Section 6.1 modified to accommodate insertion of new footnote q

1. Revised section 5.1.4 Monitoring Dose Administration to specify that subjects must be monitored for injection-related reactions and cytokine-release syndrome for a minimum of 6 hours following intratumoral injection of SL-172154.
 - New text (provided in italics) added as follows to Section 5.1.4: *All subjects must be observed for at least 6 hours after the injection.*
 - Schedule of Assessments (SOA) Table in Section 6.1: New text (provided in italics) added to footnote m as follows: *All subjects must be observed for at least 6 hours at the center after each intratumoral injection of SL-172154.*
2. The protocol is modified to include ECG monitoring at Tmax after the first dose. In addition, a predose ECG assessment on cycle 2 day 1 has been added for safety purposes after repeated dosing as no accumulation of SL172154 is expected.
 - Inclusion Criterion #9 revised in Synopsis/Section 4.1: ECG assessment inclusion criterion #9 specifies baseline QTcF interval requirement for study eligibility as ≤ 480 milliseconds
 - ECG assessments added to the SOA Table in Section 6.1 at screening, cycle 1, day 1, and cycle 2, day 1. A new footnote q added with the new text (provided in italics) as follows:

Electrocardiogram (ECG): *Local ECG machines available at the site should be used. A single ECG will be collected during screening to determine eligibility. ECGs will be obtained in triplicate for assessment of QT/QTc as outlined below (See Section 6.3.5 for additional details).*

- *Cycle 1, Day 1: Predose and 1 hour and 4 hours after ITI SL-172154*
- *Cycle 2, Day 1: Predose only*

- A new Section 6.3.5 entitled Electrocardiogram Monitoring for QTc Evaluation is now included.
- New text (provided in italics) was added to Section 9.2.4 Safety Analyses as follows: *Change from baseline QTcF will also be summarized.*

3. The maximum number of target lesions assessed per RECIST v1.1 will be 10 lesions instead of 5 lesions.

- 5 target lesions changed to 10 target lesions in Section [8.1.1](#) in the second paragraph and in Appendix [16.5.1](#) in the fifth paragraph (2 locations)
